#### 48 Assessment of Urinary Nitrogen Excretion

49 Volunteers will void urine before starting steady state exercise, with a subsequent urine sample  
50 immediately after (400-min) the conclusion steady-state exercise to measure nitrogen excretion during  
51 exercise. Urine volume will be measured and aliquots stored at  $-20^{\circ}\text{C}$  until analyzed. Total nitrogen  
52 content of the urine will be determined using pyrochemiluminescence (Antek 9000, Houston, TX).  
53

### Calculations of Carbohydrate, Fat, and Protein Oxidation

Carbohydrate, fat, and protein oxidation rates will be calculated from  $\dot{V}O_2$  (L/min),  $\dot{V}CO_2$  (L/min), and urinary nitrogen excretion rate (g/min) during the 80-min exercise bout as described by Jeukendrup and Wallis (29):

Fat oxidation (g/min) =  $1.695 \times \dot{V}O_2 - 1.701 \times \dot{V}CO_2 - 1.77 \times$  urinary nitrogen  
Carbohydrate oxidation (g glucose/min) =  $4.210 \times \dot{V}CO_2 - 2.962 \times \dot{V}O_2 - 2.37 \times$  urinary nitrogen  
Protein oxidation (g/min) =  $6.25 \times$  urine nitrogen excreted (g)/ urine collection time (min)

### Calculations of Exogenous and Endogenous Glucose Oxidation

Exogenous and plasma glucose oxidation will be calculated as (1):

Exogenous glucose (g/min) =  $\dot{V}CO_2 [(R_{exp} - R_{ref}) / (R_{exo} - R_{ref})] / k$   
Plasma glucose (g/min) =  $\dot{V}CO_2 [(R_{exp} - R_{ref}) / (R_{glu} - R_{ref})] / k$

where  $\dot{V}CO_2$  is in L/min,  $R_{exp}$  is the observed isotopic composition of expired  $CO_2$ ,  $R_{ref}$  is the isotopic composition of expired  $CO_2$  at rest before ingestion of the first dose of  $^{13}C$ -glucose,  $R_{exo}$  is the isotopic composition of the exogenous glucose ingested,  $R_{glu}$  is the isotopic composition of plasma glucose, and  $k$  (0.747 L/g) is the volume of  $CO_2$  provided by the complete oxidation of glucose. Total endogenous glucose oxidation can be calculated by subtracting exogenous glucose oxidation from total CHO oxidation. Endogenous glucose oxidation derived from muscle and liver can be determined by subtracting plasma glucose oxidation from total carbohydrate oxidation (muscle), and subtracting exogenous carbohydrate oxidation (liver) from plasma glucose oxidation (1). The first 40 min of steady-state exercise will allow for equilibration between the  $^{13}C/^{12}C$  in expired  $CO_2$  and the  $^{13}C/^{12}C$  in  $CO_2$  produced in tissues (30). Thus, endogenous glucose oxidation will only be calculated from samples obtained in the last 40 min of steady-state exercise (40 to 80 min).

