30 exogenous carbohydrate oxidation rates are achieved between 51-64% of  $\dot{V}O_{2max}$  (11). Therefore, in  
31 this previous study (2), it is possible that exogenous carbohydrate oxidation was already maximal  
32 during the normoxic exercise trials and could not increase any further during the hypoxic exercise. In a  
33 recent investigation, our laboratory sought to examine whether oxidation rates of exogenous glucose  
34 would differ during exercise performed at the same absolute intensity in normoxic and hypoxic  
35 conditions at exercise intensities eliciting less than maximal exogenous carbohydrate oxidation rates at  
36 HA. Findings from this study (unpublished) indicated that exogenous glucose oxidation diminished by  
37 46% from SL to HA when participants consumed 144 g carbohydrate while walking on a treadmill for  
38 80-min at a fixed absolute workload ( $\dot{V}O_2 = \sim 1.7 L \cdot min^{-1}$ ; 55%  $\dot{V}O_{2max}$  at HA; **Figure 1**). While  
39 exogenous glucose oxidation was lowered in our investigations, endogenous carbohydrate oxidation  
40 was numerically but not statistically higher at HA compared to SL. These data suggested that the  
41 body's ability to oxidize exogenous glucose during exercise may be compromised during acute HA  
42 exposure.

[figure not shown]
Figure 1: Carbohydrate oxidation

43  
44 Decreased insulin sensitivity is one potential mechanism for diminished ability to oxidize exogenous  
45 carbohydrate oxidation at HA (12-15). Concomitant with the suppression of exogenous carbohydrate  
46 oxidation in acute hypoxia, we also observed that blood glucose levels rose higher and remained  
47 elevated during exercise despite two to four fold higher insulin concentrations during HA exercise  
48 compared to SL (**Figure 2**). Under normal physiological conditions, elevated blood glucose levels  
49 stimulates a rise in circulating insulin to induce translocation of glucose transporter 4 (GLUT4), resulting  
50 in the uptake of glucose intake the cell. Several other investigations (12-15) have also observed this  
51 phenomenon of impaired insulin sensitivity upon acute exposure to HA in young healthy individuals.  
52 Therefore, it is possible that insulin resistance at HA may be a mechanism suppressing exogenous  
53 carbohydrate oxidation. However, little is known regarding alterations in intramuscular processes that

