### 5 B3. MILITARY RELEVANCE

6  
7  
8  
9 Service members deployed to HA regions of the world experience aerobic performance decrements.  
10 Based on findings from our previous study, one contributing factor, at least during acute exposures to  
11 HA, is a decreased ability to oxidize exogenous glucose, with no difference in total and endogenous  
12 carbohydrate metabolism. During the initial exposure to HA there appears to be a diminished insulin  
13 sensitivity in response to carbohydrate consumption, resulting in a 46% reduction in exogenous glucose  
14 oxidation during exercise compared to SL.

15 Additionally, consumption of carbohydrate at HA did not minimize declines in physical performance  
16 compared to a matched non-nutritive placebo as determined by a 2-mile time trial (Figure 3). These  
17 data indicate that while dietary carbohydrate or carbohydrate supplementation may not support  
18 exercise performance during acute HA exposure.  
19 Though it was observed that exogenous glucose  
20 oxidations was lower during exercise at HA compared  
21 to SL, the mechanism leading to diminished exogenous  
22 glucose oxidation at HA remains unclear. The purpose  
23 of this study is to define the metabolic underpinnings  
24 for lower exogenous glucose oxidation to develop  
25 appropriate dietary recommendations and/or  
26 countermeasures to support acute HA military  
27 operations.  
28  
29  
30

Figure 3: 2-mile time trial

\*Different than Sea Level;  $P < 0.05$

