### 39 **B5.8.2 Data analysis**

40  
41 Statistical analyses will be conducted using either SPSS (IBM Corp. Armonk, NY), SAS 9.3 (SAS  
42 Institute Inc., Carey, NC), or equivalent. Common descriptive statistics will be used to describe  
43 volunteer characteristics. Shapiro-Wilk tests will be used to determine normality of data. Paired t-  
44 test will be performed to determine main effects of phase (SL versus HA) for glucose turnover and  
45 glucose oxidation. Mixed model repeated measures ANOVA will be performed to determine main  
46 effects of time (baseline versus post-exercise), phase (SL versus HA) and time-by-phase  
47 interactions for glucose and insulin concentrations, GLUT4 translocation, glycogen, mRNA and  
48 microRNA, Western blots and enzyme activity. If interactions are significant, appropriate post-  
49 hoc correction will be used to examine these relationships. Correlation coefficients and multiple  
50 regression analysis will be used to evaluate relationships between study outcome measures. The  
51 alpha level will be adjusted for multiple comparisons, with the level for statistical significance set  
52 at  $P < 0.05$ .  
53

---

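### Total carbohydrate oxidation and exogenous/plasma glucose oxidation use different CO2-per-gram bases, so endogenous and muscle rates found by subtraction are too low by 7.3% of the total

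*Combined protocol and SAP*

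**What the plan says.** In Section B5.4, *Calculations of Carbohydrate, Fat, and Protein Oxidation*, the total comes from gas exchange and is labelled "Carbohydrate oxidation (g glucose/min". Its coefficients are 4.210 on VCO2, −2.962 on VO2 and −2.37 on urinary nitrogen. The companion fat equation has 1.695 on VO2 and −1.701 on VCO2.

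The next subsection, *Calculations of Exogenous and Endogenous Glucose Oxidation*, converts labelled CO2 to grams with a constant k, given as "0.747 L/g) is the volume of" CO2 from complete oxidation of glucose. Exogenous and plasma glucose oxidation both use k. The derived rates follow by subtraction: "Total endogenous glucose oxidation can be calculated by subtracting exogenous glucose oxidation from total CHO oxidation". Muscle is total minus plasma, and liver is plasma minus exogenous. Neither subsection converts between the two gram scales.

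Section B5.8.2 plans paired t-tests for "main effects of phase (SL versus HA) for glucose turnover and" glucose oxidation.

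**The concern.** A difference between two rates has a meaning only if both are in the same unit. Here both carry the label grams of glucose, but the coefficients suggest that a gram of total carbohydrate corresponds to more CO2 than a gram of exogenous or plasma glucose. If so, total minus exogenous and total minus plasma are biased downwards.

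The error is a fixed fraction of the total, so it takes up more of the derived rate where exogenous glucose supplies a larger share. The plan expects that at SL. Absolute endogenous and muscle rates, the split of carbohydrate between sources, and percent changes from SL to HA would all be affected. Section B3 rests part of the rationale on such quantities, reporting lower exogenous oxidation "with no difference in total and endogenous" carbohydrate metabolism.

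**Working it through.** **1. Reproduce k.** One mole of glucose gives 6 mol CO2: 6 × 22.4 / 180 = 0.747 L/g. This matches the plan, so k is a pure-glucose basis, equal to 1/0.747 = 1.339 g per L CO2.

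**2. Basis of the total.** At RER 1.0 with zero nitrogen, the total is 4.210 − 2.962 = 1.248 g per L CO2, or 1/1.248 = 0.801 L/g. The plan's fat equation is then 1.695 − 1.701 = −0.006 g per L, which is essentially zero, so nearly all the CO2 is assigned to carbohydrate.

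**3. Ratio.** 0.8013 / 0.747 = 1.0727. Changing the carbohydrate basis rescales the whole total, nitrogen term included, so the factor applies at every RER.

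**4. Closure check.** Suppose RER is 1.0, nitrogen is zero and all expired CO2 comes from the drink. True endogenous oxidation is zero. The plan gives total 1.248 × VCO2, exogenous 1.339 × VCO2, and hence endogenous −0.091 × VCO2.

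**5. Illustration of size.** The documents give no RER and no absolute exogenous rate, so these inputs are partly assumed:

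- VO2 is 1.7 L/min, from the previous study in Section B2.
- RER is assumed to be 0.85 to 1.00, with zero nitrogen.
- Exogenous rates are inferred by treating the fall of 14 g per 40 min (Section B5.8.1) as the same fall that Section B2 reports as "46% from SL to HA when participants consumed 144 g carbohydrate". This gives SL 14 / 0.46 / 40 = 0.761 g/min and HA 0.761 × 0.54 = 0.411 g/min.

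Plan total = 1.7 × (4.210 × RER − 2.962). Consistent total = plan total × 1.0727. Endogenous = total − exogenous. All rates are in g/min.

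| RER | Plan total | Shortfall | SL endogenous: plan / consistent | SL error | HA endogenous: plan / consistent | HA error |
|---|---|---|---|---|---|---|
| 0.85 | 1.048 | 0.076 | 0.287 / 0.363 | −21.0% | 0.637 / 0.713 | −10.7% |
| 0.90 | 1.406 | 0.102 | 0.645 / 0.747 | −13.7% | 0.995 / 1.097 | −9.3% |
| 0.95 | 1.764 | 0.128 | 1.003 / 1.131 | −11.3% | 1.353 / 1.481 | −8.7% |
| 1.00 | 2.122 | 0.154 | 1.361 / 1.515 | −10.2% | 1.711 / 1.865 | −8.3% |

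With an assumed 0.01 g/min of nitrogen at RER 0.85, the errors become −22.0% (SL) and −10.8% (HA).

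**6. Shares and contrasts.**

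- Exogenous share at SL, RER 0.90: 0.761/1.406 = 54.1% on the plan's basis, against 0.761/1.508 = 50.5% on a consistent basis.
- SL-to-HA change in endogenous oxidation, RER 0.90 in both phases: 0.995/0.645 gives +54%, against 1.097/0.747 giving +47%. The absolute change is +0.350 g/min either way.
- RER 0.90 at SL and 0.95 at HA: 1.353 − 0.645 = 0.708 g/min, against 1.481 − 0.747 = 0.734 g/min. The contrast is off by 0.026 g/min, or 1.0 g per 40 min.

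**The case against.** The strongest reply is that endogenous carbohydrate, muscle carbohydrate above all, is largely glycogen. The plan's basis of 0.801 L/g lies between glucose (0.747) and glycogen (about 0.829, from 6 × 22.4 / 162.1), so the total may be a mixed-carbohydrate figure and only its label wrong. With endogenous oxidation expressed as grams of glycogen, the same illustration gives 0 to 12% too low at SL, and 1% too low to 2% too high at HA. The smaller gap is real, but the defence does not remove the fault. It contradicts the plan's stated unit, still subtracts grams of glucose from grams of something else, and leaves an error that differs by phase.

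Second, no planned test is shown to be materially affected. Section B5.8.2 names neither source shares nor percent changes, and the absolute SL–HA contrast is off only by 7.3% of the difference in totals. This stands, and it limits the importance of the point.

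Third, the 7.3% depends on taking the basis at RER 1.0. Where the plan's fat equation is exactly zero, VO2/VCO2 = 1.701/1.695 = 1.0035. The total is then 4.210 − 2.962 × 1.0035 = 1.238 g per L CO2, which is 0.808 L/g and a factor of 1.082. The gap becomes 8.2%, so 7.3% is the lower of the two readings, and a factor of 1.073 would leave about 0.8% uncorrected on that reading.

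Fourth, the phase-specific percentages rest on an assumed RER and on equating two figures that the documents do not say describe the same measure. That also stands. The 7.3% itself needs neither.

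Fifth, rescaling only this study would offset it from the previous one. That is a real cost, but it can be handled.

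**Conclusion.** The plan is internally inconsistent and should be corrected. In its stated unit, total endogenous and muscle oxidation are too low by 7.3% of the calculated total. This follows from the printed coefficients and k alone, with the basis taken at RER 1.0.

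As a fraction of the endogenous rate itself, the error is 10 to 21% at SL and 8 to 11% at HA, on the assumptions in step 5 of the working.

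The consequences are confined to secondary, derived quantities: absolute endogenous and muscle rates, source shares and percent changes. The absolute SL–HA contrast nearly cancels if totals are similar, as Section B3 reports for the previous study. Exogenous oxidation is unaffected because it does not use the total; plasma and liver rates are unaffected because every term in them uses k.

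**What to change.** Before subtracting, multiply the whole gas-exchange total, nitrogen term included, by 0.801/0.747 = 1.073. Equivalently, use 4.516 × VCO2 − 3.177 × VO2 − 2.54 × urinary nitrogen. Keep the grams-of-glucose label, which then matches k, and add one sentence stating the conversion and that endogenous and muscle rates are in glucose equivalents.

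The cost is one constant in the calculation sheet and one sentence of text, with no new data. The drawback is comparability: total, endogenous and muscle values would be offset by 7.3% of the total from earlier work computed the old way. Sections B4 and B5.2.1 intend this study to confirm, and be compared with, the previous one. The same factor should therefore be applied to that study's totals if it used these equations, which the documents do not say.

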**Exercise Protocol Day**

Two catheters will be placed into the lower arm (one in each arm). One arm will be used for infusion of 6,6-[H2] glucose tracer and the other will be used for blood sampling under resting and exercise conditions. Following an initial blood and breath sample collection to determine background enrichments, a primed, continuous infusion of 6,6-[H2] glucose will begin (prime, 82.2 μmol·kg; continuous rate, 0.78 μmol·kg·min, **Figure 4**) (24, 25). Volunteers will complete 80-min of steady-state exercise on a treadmill at 55 ± 5% of their VO2peak determined at HA, performing the same absolute work under both study conditions. V̇O2, V̇CO2, HR, and SaO2 will be measured at approximately 320, 330, 340, 360, 380, and 395 min. During exercise volunteers will consume a CHO beverage at 1.8 g·min to examine the impact of altitude exposure on exogenous carbohydrate oxidation efficiency. Drinks will contain 145 g glucose, with a total volume of 1450 mL. The drink will be consumed in four boluses throughout the 80-min of steady-state exercise (320, 340, 360, and 380-min). The first bolus will be 550 mL, with the remaining three being 300 mL. The CHO beverage consumed during exercise will be enriched with 200 mg U-C-glucose (Cambridge Isotope Laboratory, Andover, MA, USA) to increase the isotopic enrichment well above natural levels and optimize the measurement of exogenous carbohydrate oxidation. Before exercise, during the HA phase, volunteers will be exposed to hypobaric hypoxic conditions for 5-hrs to mimic our previous investigation. Muscle samples will be obtained using percutaneous muscle biopsy, taken from the vastus lateralis using a 5-mm Bergstrom needle with manual suction while the volunteer is under local anesthesia (1% lidocaine) according to the approved USARIEM SOP (26, 27). Muscle samples will be collected before (300 min) and immediately (420 min) after 80-min of steady state exercise during both the SL and HA protocol study days. The two muscle biopsy collections will occur from one incision each protocol day. Following a minimum 7-d washout period, volunteers will return to the laboratory to complete the second arm of the investigation. A total of four muscle biopsies will be conducted per volunteer, two per protocol day, with one incision made on each leg.

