#### 19 Breath Sample Processing for Isotopic Enrichment

20 The natural enrichment of the glucose ingested and the  $^{13}\text{C}/^{12}\text{C}$  in expired gas samples will be analyzed  
21 using isotope-ratio mass spectroscopy (Metabolic Solutions, Inc., Nashua, NH). Breath samples will be  
22 collected at approximately 320, 330, 340, 350, 360, 365, 370, 375, 380, 385, 390, and 395-min to  
23 determine exogenous carbohydrate oxidation using single-patient breath collection bags (Quin-Tron  
24 Instrument Company, Milwaukee, WI, USA). A baseline breath sample will also be collected prior to  
25 correct for background of naturally occurring  $^{13}\text{C}$ . All breath samples will be transferred to 10 mL  
26 evacuated tubes.  
27

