## 27 **B5.8 Statistical Analysis**

### 28 **B5.8.1 Sample Size Estimation**

29  
30  
31 Statistical power and sample size were determined from the effect size of exogenous  
32 carbohydrate oxidation ( $-14 \pm 8$  g/40-min exercise) that we previously observed at HA compared  
33 to SL. Using this information the sample size necessary to determine statistical significance  
34 between intervention arms is 7, with an alpha of 0.05 and 80% power. To account for greater  
35 variance in the response to altitude between volunteers and increased study power to 90%, 10  
36 volunteers will be enrolled to complete this investigation. Based on our previous studies we  
37 request to consent 30 individuals to complete 10.  
38

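### Does limiting only endogenous oxidation to the last 40 min leave exogenous oxidation, the main outcome, on unequilibrated breath samples?

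*Combined protocol and SAP*

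**What the plan says.** The section on calculating exogenous and endogenous glucose oxidation (B5.4) computes exogenous and plasma glucose oxidation from the isotopic composition of expired CO2. On timing it says "The first 40 min of steady-state exercise will allow for equilibration between the" breath and tissue ratios, and concludes: "Thus, endogenous glucose oxidation will only be calculated from samples obtained in the last 40 min of steady-state exercise (40 to 80 min". It also gives the derivation: "Total endogenous glucose oxidation can be calculated by subtracting exogenous glucose oxidation from total CHO oxidation".

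The breath-sampling section has samples "collected at approximately 320, 330, 340, 350, 360, 365, 370, 375, 380, 385, 390, and 395-min to" "determine exogenous carbohydrate oxidation using single-patient breath collection bags (Quin-Tron". It names no averaging window. Drinks are taken at "320, 340, 360, and 380-min", so exercise starts at 320 min on the protocol clock and its last 40 min run from 360 to 400 min.

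The section on carbohydrate, fat and protein oxidation uses gas exchange and "urinary nitrogen excretion rate (g/min) during the 80-min exercise bout". B5.8.1 powers the study on a change in exogenous oxidation of -14 ± 8, expressed in "g/40-min exercise) that we previously observed at HA compared" to sea level. B5.8.2 names a paired t-test for glucose oxidation without giving a window.

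**The concern.** The reason for the limit applies first to the quantities the sentence leaves out. Exogenous and plasma oxidation contain the expired-CO2 ratio directly; total endogenous oxidation contains it only through the exogenous term that is subtracted. Read literally, the plan protects the derived quantity and leaves its source unprotected.

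The primary objective is to confirm that exogenous oxidation falls at altitude. If early samples entered that outcome, labelled CO2 still filling the body pool would not yet appear in breath, and grams oxidised would be understated. The result might then not match the earlier study's figure, which is per 40 min, and endogenous oxidation could sit on a different window from the terms it is built from. An unstated window also lets an analyst choose between 0-80 and 40-80 min after seeing the data.

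**Working it through.** **1. Which window do the documents imply?** Exercise runs from 320 to 400 min.

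- *Subtraction.* Endogenous = total carbohydrate - exogenous. If the left side is computed only over 40-80 min, the exogenous term must be computed there too.
- *Unit.* The powered effect is in g per 40 min. A full-bout total would be in g per 80 min.
- *Sampling density.* Samples before 360 min: 320, 330, 340, 350 (4 samples, 10 min apart). From 360 min: 360, 365, 370, 375, 380, 385, 390, 395 (8 samples, 5 min apart). The schedule tightens exactly at 40 min of exercise.
- *The 80-min phrase.* It occurs with the gas-exchange and urinary-nitrogen rates. Urine is voided before exercise and collected once at 400 min, so nitrogen can only be a whole-bout rate. Oxygen uptake and CO2 output are measured serially, so a 40-80 min total carbohydrate rate is available.

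No section states a 0-80 min analysis of exogenous oxidation.

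**2. The plan's sample size.** Inputs from B5.8.1: difference 14 g, SD 8 g, alpha 0.05 (two-sided assumed), 7 volunteers for 80% power, 10 enrolled. For a paired t-test, power comes from the noncentral t with n - 1 degrees of freedom and noncentrality (14/8)√n:

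| n | Power |
|---|---|
| 5 | 82.8% |
| 7 | 96.8% |
| 10 | 99.8% |

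The minimum for 80% is 5, so the stated 7 is conservative if 8 is the SD of paired differences. Seven gives 80% when that SD is 11.0, and 10 gives 90% when it is 12.1. Stating the window changes none of this.

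**3. If the whole bout were used.** The documents give no equilibration constant. Assume a first-order lag, constant production of labelled CO2, and a fraction q equilibrated at 40 min. Then τ = -40/ln(1 - q), and mean recovery over 0 to T is 1 - (τ/T)(1 - e^(-T/τ)).

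| q | τ (min) | 0-40 min | 0-80 min | Understatement over 80 min |
|---|---|---|---|---|
| 0.90 | 17.4 | 0.609 | 0.785 | 21.5% |
| 0.95 | 13.4 | 0.683 | 0.834 | 16.6% |
| 0.99 | 8.7 | 0.785 | 0.891 | 10.9% |

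**4. Effect on the comparison.** If recovery is a common factor c in both phases, the paired statistic is c·d̄ / (c·s/√n) = d̄ / (s/√n). The test and the percentage reduction are unchanged; only grams shrink.

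A harsher case shrinks the mean and leaves the SD alone: 14 × 0.785 = 10.99 g. With SD 8 and n = 10, power is 97.0%. With the SD of 12.1 implied by the plan's 90% target, the same case moves power from 90.1% to 72.5%. That last figure needs three things together: the 80-min reading, the slowest assumed lag, and an SD that does not shrink with the mean.

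**The case for a change.** The strongest case for a change is that an expert's ability to infer the window does not fix it in advance. The study aims to confirm an earlier result, exogenous oxidation is the only measure used for sample size, and two analysts could report different gram totals without contradicting any sentence in the plan. The earlier 46% fall is described for an 80-min walk, and B5.8.1 does not say which 40 min its figure covers. One added sentence would close the question and needs no new samples.

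Much of this stands. The limit is written for endogenous oxidation alone, its reason covers exogenous and plasma oxidation equally, and B5.8.2 gives no window. What does not stand is the claim that the main outcome would use unequilibrated samples or an unpowered window. A list of collection times does not define an averaging window, and the per-40-min unit is evidence for the late window, not a mismatch with it. The freedom to choose is also narrow: a full-bout exogenous value would be at odds with the section's own equilibration statement, with the powered unit, and with the 40-80 min endogenous value reported beside it.

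**Conclusion.** The concern identifies incomplete wording, not a flaw in the analysis. An analyst applying the stated equilibration reason and the subtraction formula would compute exogenous and plasma oxidation over 40-80 min, which is what an amendment would ask for. The number of volunteers and the sampling schedule would be the same either way.

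The 11 to 21.5% understatement depends on a reading the plan does not state and on kinetics it does not give. No difference in lag between sea level and altitude is shown. Matching the absolute workload gives some reason to expect similar CO2 output in the two phases, but the documents contain no data on this. A common proportional loss leaves the test unchanged. Shrinking the mean alone leaves power at about 97% with 8 g as the SD of paired differences, and it falls materially only if a larger SD is added. The conclusion also assumes that the earlier 14 g came from the last 40 min of exercise, which is the natural reading but is not stated.
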